### 3.5.4 Analysis Populations

#### 3.5.4.1 Immunogenicity Analysis Populations

##### Per Protocol Immunogenicity Population

The per-protocol immunogenicity (PPI) analysis populations will serve as the primary populations of subjects for the analysis of immune responses to each of the 9 HPV types (6, 11, 16, 18, 31, 33, 45, 52, and 58). The PPI analysis populations are HPV type-specific, i.e., each HPV type has its own PPI analysis population. To be included in a particular HPV type-specific PPI analysis population, subjects must:

- Have received all 3 vaccinations of the correct dose of GARDASIL®9 within acceptable day ranges (See Table 4).
- Have evaluable serology results at Day 1 and Month 7 based on serum samples collected within acceptable day ranges (See Table 5).
- Be seronegative to the appropriate HPV type at Day 1.
- Have no protocol deviations that could interfere with the evaluation of subject's immune response to GARDASIL®9.

To be included in the PPI analysis population for any vaccine HPV type, subjects need to be seronegative to that specific type at Day 1. The final determination of protocol deviation categories deemed as having potential to interfere with evaluation of immune response to GARDASIL®9 will be made prior to database lock and will be recorded in a separate study document.

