#### **3.5.1 In-house Blinding**

All subjects in this study will receive GARDASIL®9; the study is thus open-label.

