### **3.5.5 Statistical Methods**

#### **3.5.5.1 Immunogenicity Analyses**

The primary analyses of immunogenicity will be conducted in the Per Protocol Immunogenicity (PPI) population as defined in Section 3.5.4.1. Immunogenicity data will be analysed separately for HIV and SOT patients. The potential influence of factors such as immunosuppressive therapy and time after transplantation for SOT patients and CD4-count and antiretroviral therapy for HIV patients will be estimated.

- Seroconversion

The primary outcome, seroconversion, defined as changing serostatus from seronegative at Day 1 to seropositive (antibody titre above seroconversion cut-off) by 4 weeks after Dose 3, will be described with 95% CI. Differences with historical controls will be determined with a test for binary (seroconversion or not) proportions.

- GMT

All titers will be log transformed and the antilog of the mean will be calculated to obtain the GMT. GMT will be described with 95%CI. GMTs of immunocompromised patients will be compared with GMTs of historical controls with a one sample *t*-test, comparing month 7 GMTs for each component.

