### **3.5.6 Sample Size and Power Calculations**

Based on an expected seroconversion rate of 80%, a sample size of 170 transplant patients allows to estimate the proportion of protected transplant patients with precision (95% confidence interval) of  $\pm 6\%$  (10).

Furthermore, based on an expected seroconversion rate 85-91%, a sample size of 140 HIV-patients allows to estimate the proportion of protected patients with precision (95% confidence interval) of  $\pm 6\%$  and 5% respectively (7). Based on expected differences in GMT to healthy populations, a sample size of 140 HIV-patients allows to estimate the GMTs HPV type 6, 11, 16 and 18 with a power of 0.38, 0.82, 1 and 1, respectively (7, 19).

Due to difficulties in the recruitment of HIV patients without genital warts a recalculation of the sample size was done. With a total sample size of  $n=100$ , a majority of whom will have no history of HPV-lesions, we expect to be able to use the data of at least 80 patients for the analysis seroconversion of each HPV type under study. Seroconversion rates of 95-99% for HPV types 6, 11 and 16 can then be

estimated with a margin of error of  $\pm 4.8\%$  -  $2.2\%$ , and the anticipated seroconversion rate of 90% for HPV type 18 with a margin of error of  $\pm 6.6\%$ .

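### The open-ended deviation criterion for the primary (PPI) set is tied only to database lock, which in an open-label single-arm trial does not keep Month 7 serology from those who fix it

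*Combined protocol and SAP*

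**What the plan says.** Section 3.5.5.1 states: "The primary analyses of immunogenicity will be conducted in the Per Protocol Immunogenicity (PPI) population". Section 3.5.4.1 sets four conditions for entry to each type-specific PPI set.

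- Three are fixed in the protocol: three correct doses within the Table 4 day ranges; evaluable Day 1 and Month 7 serology within the Table 5 ranges; and seronegativity to the type at Day 1.
- The fourth is open: "Have no protocol deviations that could interfere with the evaluation of" the subject's immune response. No categories follow. Their final determination "will be made prior to database lock and will be recorded in a separate study document".

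Section 3.5.1 says: "All subjects in this study will receive GARDASIL®9; the study is thus open-label". Section 3.1.11 likewise marks blinding as not applicable. Section 3.3 sends the assays to an external laboratory but does not say when results are released, or to whom.

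Two other provisions bear on the point. Section 3.5.4.1 plans a supportive analysis in all type-specific naïve subjects with serology (ANSS), which keeps subjects with these deviations. Section 3.5.5.3 (Subject Accounting) will tabulate reasons for exclusion from the PPI sets. The seropositive/GMT population carries the same open criterion as the PPI sets.

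**The concern.** In a blinded randomised trial, settling deviations before lock protects the analysis because allocation is still hidden. Here every subject has the same treatment, so the Month 7 serostatus is the only information that could bias the choice, and a deadline tied to lock does not address access to it.

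The choice also calls for judgement. Section 3.1.4, for example, asks that corticosteroids, immunosuppressives, immune globulins and blood products be avoided only where possible, so whether such use counts as an interfering deviation must be decided. The plan itself expects immunosuppression to affect response (sections 2.5.1 and 3.5.5.1).

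The direction matters. The hypotheses in section 2.2.1 are that rates are similar to historical controls, and section 3.5.5.1 gives no margin: "Differences with historical controls will be determined with a test for binary (seroconversion or not) proportions". Losing non-seroconverters from the primary set raises the rate and so favours the hypothesised conclusion wherever the observed rate lies below the control rate.

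**Working it through.** **Inputs.** All from section 3.5.6 unless noted.
- SOT: 80% expected, N = 170, stated precision ±6%.
- HIV: at least 80 evaluable per type; 90% expected for HPV 18 (stated ±6.6%); 95–99% for HPV 6, 11 and 16 (stated ±4.8% to ±2.2%).
- 95% confidence level (section 3.5.5.1).
- Historical control rate: not given. Assumed range 95% to 99%.
- Number of subjects in open deviation categories: not given. Small numbers are used for illustration.

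**Step 1: reproduce the plan's precision.** Half-width = 1.96 × √(p(1−p)/n).
- SOT: 1.96 × √(0.80 × 0.20/170) = 6.01%.
- HIV, HPV 18: 1.96 × √(0.90 × 0.10/80) = 6.57%.
- HIV at 95% and 99%, n = 80: 4.78% and 2.18%.

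All agree with the stated figures.

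**Step 2: bound the effect of exclusions.** Let x of n subjects seroconvert and let k be excluded. The upper bound, with all k non-seroconverters, is x/(n−k). The lower bound, with all k seroconverters, is (x−k)/(n−k).

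| Cohort | Planned | k | Upper bound | Lower bound |
|---|---|---|---|---|
| HIV, HPV 18 | 72/80 = 90.0% | 2 | 72/78 = 92.3% | 70/78 = 89.7% |
| HIV, HPV 18 | 72/80 = 90.0% | 4 | 72/76 = 94.7% | 68/76 = 89.5% |
| SOT | 136/170 = 80.0% | 4 | 136/166 = 81.9% | 132/166 = 79.5% |
| SOT | 136/170 = 80.0% | 12 | 136/158 = 86.1% | 124/158 = 78.5% |

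At the upper bound, 6 HIV exclusions (7.5% of 80; 72/74 = 97.3%) or 12 SOT exclusions (7.1% of 170) move the rate by at least the full stated margin.

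**Step 3: effect on the comparison, HIV HPV 18.** Two-sided exact binomial p against a fixed assumed control rate, at the upper bound:

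| Assumed control rate | 72/80 | 72/78 | 72/76 |
|---|---|---|---|
| 95% | 0.063 | 0.29 | 0.79 |
| 97% | 0.003 | 0.030 | 0.29 |
| 98% | 0.0002 | 0.005 | 0.066 |
| 99% | <0.0001 | 0.0001 | 0.007 |

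With four exclusions the result crosses 0.05 at 97% and 98%. It does not at 95% (already non-significant) or at 99% (still significant).

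**Step 4: the benign case.** If a category covering 4 of the 80 HIV subjects were unrelated to response, the chance that all four were non-seroconverters is C(8,4)/C(80,4) = 70/1,581,580, or about 0.004%. The expected rate after exclusion stays at 90.0%, with a standard deviation of about 0.8 points.

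**The case against.** The strongest reply has four parts.

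1. **The rule fixes categories, not subjects.** A category removes everyone in it, responders included, and each subject must have an actual deviation. Step 4 shows that a category unrelated to response hardly moves the rate. If a category is related to response, excluding it may be exactly what a per-protocol set is for. This stands: the upper bounds are worst cases, not forecasts. It does not answer the timing point, because categories correlated with response are the ones whose choice could be swayed by seeing the result.

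2. **Fixing deviations before lock is ordinary practice, and an earlier list is not ruled out.** True. But the practice normally relies on blinding, and here only the final determination has a deadline.

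3. **The documents are silent rather than permissive.** The assays are run externally, no text says when results arrive, and the separate document might restrict access. A reader might infer that the team plans to choose exclusions with serostatus in view; nothing supports that. What stands is that no stated safeguard prevents it.

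4. **Selective exclusion would leave a trail.** The ANSS analysis retains these subjects, and exclusion reasons are tabulated. This helps in part. But ANSS also drops the vaccination windows, accepts serum 21 to 105 days after Dose 3 rather than 21 to 49, and requires joint seronegativity for HPV 6 and 11. A gap between PPI and ANSS therefore could not be put down to the deviation categories alone. The tabulation shows reasons, but not what was known when they were set.

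**Conclusion.** The point holds in a limited form. One of the four PPI criteria is open, and its only timing rule does not separate the choice of categories from the primary outcome.

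Three stronger readings are tempting and should not be drawn:
- **That all PPI exclusions can be settled late.** Dose, windows and baseline serostatus are prespecified.
- **That the primary result everywhere rests on a handful of non-responders.** That fits the HIV cohort at 90–99% for HPV 6, 11, 16 and 18. SOT is planned at 80% of 170, about 34 non-seroconverters, where four worst-case exclusions shift the rate by only 1.9 points.
- **That a few exclusions would overturn the comparison with controls.** This depends on an assumed control rate; of the four tried, it happens at two.

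The worst-case shift for HPV 18 in HIV patients is 4.7 points with four exclusions, inside the plan's own ±6.6. It assumes that the planned rates are met exactly and that every excluded subject is a non-seroconverter. The p-values further assume an exact test against a fixed control rate, which the plan does not specify. The gap is worth closing because the affected set is the primary one and the remedy is small.

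**What to change.** In section 3.5.4.1, replace the database-lock deadline for the deviation categories with: *before any Month 7 serology result is released to those who determine the categories, and in any case before database lock*. Date and sign the separate study document to show this. Apply the same rule to the identical criterion for the seropositive/GMT population.

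If Month 7 results have already been released, have both the categories and the subject-level decisions made by people without access to them, and record that.

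Cost: an arrangement with the external laboratory or the data manager to hold or mask Month 7 results until sign-off, plus the amended sentence and a dated signature. Sample size and planned precision do not change.

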**Table 4: Acceptable Day ranges for Vaccination Visits**

Dose of 9vHPV Vaccine Scheduled for Injection	Protocol Specified Visit Window for SOT group	Day Range for Inclusion in Statistical Analysis for SOT group (Relative to Day 1 † )	Protocol Specified Visit Window for HIV group	Day Range for Inclusion in Statistical Analysis for HIV group (Relative to Day 1 † )
Dose 1	Day 1 †	0	Day 1 †	0
Dose 2	Month 2 ± 4 weeks	30 to 90	Month 2 (-4 weeks / +2 weeks)	30 to 75
Dose 3	Month 6 (-1 week / +4 weeks)	170 to 210	Month 6 ± 4 weeks	150 to 210

† Day 1 refers to the date when Dose 1 of the study vaccine is injected. For vaccinations after Day 1, the day ranges for inclusion in the statistical analysis are wider than the protocol-specified visit windows primarily to account for differences at the study sites in counting months (e.g., 1 calendar month versus 30 days versus 4 weeks).

9vHPV, 9-valent human papillomavirus.

**Table 5: Acceptable Day Ranges for Collection of Serum Samples**

Study Visit	Target Collection Day (Relative to Day 1 † )	Day Range for Inclusion in Statistical Analysis †
Day 1	0	-14 to 0 (Relative to Day 1) ‡
Month 7	30 days after Dose 3	21 to 49 after Dose 3 §

† Day 1 refers to the date when dose 1 of study vaccine is injected. For Month 7, indicated target collection/day range is relative to date of injection of Dose 3 of study vaccine.
 
‡ Applies to both the PPI and ANSS analysis populations.
 
§ Applies to the PPI analysis population only. The day range for the ANSS analysis population is 21 to 105 days after dose 3.
 
ANSS = All type-specific naïve subjects with serology; PPI = Per-protocol immunogenicity.
		

#### All Type-Specific Naïve Subjects with Serology Population

A supportive immunogenicity analysis will be carried out on the all type-specific naïve subjects with serology (ANSS) analysis population. The ANSS analysis populations are HPV type-specific similar to the PPI analysis populations. To be included in these sets of subjects, subjects must:

- Have received all 3 vaccinations of GARDASIL®9;
- Have evaluable serology results at Day 1 and Month 7 based on serum samples collected within acceptable day ranges (See Table 5);
- Be seronegative to the appropriate HPV type at Day 1.

To be included in the ANSS analysis population for HPV 6 and 11, subjects must be seronegative to both HPV 6 and 11 at Day 1. To be included in the ANSS analysis population for any other vaccine HPV type, subjects need to be seronegative to that specific type at Day 1.

Unlike the PPI analysis populations, ANSS analysis populations will not exclude subjects who had protocol deviations deemed as having potential to interfere with evaluation of immune response to GARDASIL®9. In addition, no day ranges on the timing of the vaccination will be applied.

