- The expected seroconversion rates that were used for the sample size calculation were retrieved from published data of patients with a CD4-count of 200-350 cells/mm^2. However, 92% of the patients that are currently included have a CD4-count of  $> 350$  cells/mm^2, which makes seroconversion rates in patients with more than 350 CD4+ cells/mm^2 more applicable (1). Published seroconversion rates in these patients are 95%-99% for HPV types 6, 11 and 16 and 90% for HPV-18.
- This sample size calculation does not take in to account that patients might be seropositive to certain HPV-types at baseline and that their data will be excluded for the analysis of the seroconversion outcome of the corresponding HPV-type. Seroprevalence to different HPV-types in previous studies on the safety and immunogenicity of the quadrivalent HPV-vaccine in HIV patients ranged from 13% to 45% for the different vaccine HPV-types (1-3).
- In order to maximize the number of eligible subjects, we amend the protocol to also **include patients with a history of abnormal PAP-smears without treatment or genital warts**. We believe that this allows us to reach a total sample size of at least 100 HIV-patients. Patients who are seropositive for a given HPV-type at baseline will

still be excluded for the analysis of seroconversion of that particular type but will still be useful for the analysis of the other HPV-types. Knowing that in HIV-patients the expected seroconversion rate of HPV-18 is relatively lower than the seroconversion rates of HPV types 6, 11 and 16, maximizing the number of eligible subjects for the analysis of this type is especially beneficial in order to obtain a reasonable margin of error. Enrolling patients with history of genital warts, who are most likely seropositive to HPV types 6 or 11, still allows us to increase the number of HPV-18 seronegative patients. In addition, clinical presentation of HPV infection does not necessarily implicate seropositivity to HPV.

- **With a total sample size of n=100, a majority of whom will have no history of HPV-lesions, we expect to be able to use the data of at least 80 patients for the analysis seroconversion of each HPV type under study. Seroconversion rates of 95-99% for HPV types 6, 11 and 16 can then be estimated with a margin of error of  $\pm 4.8\%$  -  $2.2\%$ , and the anticipated seroconversion rate of 90% for HPV type 18 with a margin of error of  $\pm 6.6\%$ .**

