#### 2.4. Subject exclusion criteria

To be included and receive the first study vaccination, subjects should not have any exclusion criteria. For items with an asterisk (\*), if the subject meets these exclusion criteria, the Day 1 visit may be rescheduled for a time when these criteria are not met.

1. Subject has a history of an abnormal Pap test or abnormal cervical biopsy results (showing cervical intraepithelial neoplasia or worse) or cervical disease (i.e., surgical treatment for cervical lesions).
2. **Patient medical history regarding HPV lesions:**
  - a. **Exclusion criterion for HIV patients:** Subject has history of high grade Anal Intraepithelial Neoplasia, high grade Vulvar Intraepithelial Neoplasia or high grade Vaginal Intraepithelial Neoplasia.
    - history of anal or peri-anal condyloma is allowed
  - b. **Exclusion criterion for SOT patients:** Subject has history genital warts, Anal Intraepithelial Neoplasia, Vulvar Intraepithelial Neoplasia or Vaginal Intraepithelial Neoplasia.
3. Subject has a history of known prior vaccination with an HPV vaccine, i.e., received a marketed HPV vaccine, or has participated in an HPV vaccine clinical study and has received either active agent or placebo.
4. Subject is pregnant (as determined by serum or urine pregnancy test).
5. Subject is, at the time of signing ICF, a user of recreational or illicit drugs or has had a recent history (within the last year) of drug or alcohol abuse or dependence. Alcohol abusers are defined as those who drink despite recurrent social, interpersonal, and/or legal problems as a result of alcohol use.

6. Subject has a history of severe allergic reaction, including known allergy to any vaccine component, including aluminum, yeast, or BENZONASE® (nuclease, Nycomed [used to remove residual nucleic acids from this and other vaccines]) (e.g., swelling of the mouth and throat, difficulty breathing, hypotension or shock) that met the criteria for serious adverse experiences defined in this protocol.
7. **Patient's condition**

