### Baseline HPV Status

A serum sample will be collected from all subjects at the Day 1 visit for the purpose of assessing baseline HPV serostatus to the 9vHPV vaccine HPV types (HPV 6, 11, 16, 18, 31, 33, 45, 52, and 58). A subject will be considered seropositive to a given HPV type at Day 1 if the subject's anti-HPV titre is greater than or equal to the corresponding serostatus cutoff for that HPV type or seronegative to a given HPV type at Day 1 if the subject's anti-HPV titre is less than the corresponding serostatus cutoff for that HPV type. For each HPV type, the proportions of subjects who are seronegative or seropositive will be summarized for both HIV and SOT patients.

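### For HPV 6 and 11 the supportive ANSS set has a stricter Day 1 serostatus rule than the primary PPI set, so it does not contain PPI and a PPI–ANSS difference mixes two changes

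*Combined protocol and SAP*

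**What the plan says.** The primary set, under Per Protocol Immunogenicity Population in section 3.5.4.1, uses one baseline rule for all nine types: "for any vaccine HPV type, subjects need to be seronegative to that specific type at Day 1".

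The supportive set is defined later in the same section. Its bulleted criteria also ask for seronegativity to the type in question. The next paragraph then overrides this for two types: "for HPV 6 and 11, subjects must be seronegative to both HPV 6 and 11 at Day 1". The other seven types keep the single-type rule.

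In other respects ANSS is the looser set. On deviations the plan says: "Unlike the PPI analysis populations, ANSS analysis populations will not exclude subjects who had protocol deviations". No vaccination day ranges apply. On the Month 7 sample, a footnote to Table 5 says: "The day range for the ANSS analysis population is 21 to 105 days after dose 3"; PPI accepts 21 to 49 days.

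The Rationale for Amendment 1 says that a patient seropositive to one type is left out for that type "but will still be useful for the analysis of the other HPV-types". No section gives a reason for treating HPV 6 and 11 as a pair in ANSS but not in PPI.

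**The concern.** A supportive set with looser entry rules normally shows whether the primary result depends on excluding off-schedule patients and those with protocol deviations. It can do this cleanly only if it keeps every primary-set patient and adds those whom the stricter rules removed. For HPV 6 and 11 it adds some patients and drops others. If the PPI and ANSS results differ for these types, the reader cannot tell whether relaxed conduct rules or a narrower baseline population is responsible. If they agree, two opposite effects may have cancelled.

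There is also a gap in coverage. An off-window patient who is negative to HPV 6 and positive to HPV 11 is in neither set for HPV 6, although ANSS otherwise takes in off-window patients.

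The issue is likely to matter most in the HIV group. Under section 2.4 "history of anal or peri-anal condyloma is allowed" for HIV patients, and the Rationale for Amendment 1 expects patients with genital warts mostly to be seropositive to HPV 6 or 11. SOT patients with a history of genital warts remain excluded.

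**Working it through.** **Step 1: compare the definitions (section 3.5.4.1, Tables 4 and 5).**

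| Criterion | PPI | ANSS | ANSS relative to PPI |
|---|---|---|---|
| Doses | three, correct dose | three | looser |
| Vaccination day ranges | Table 4 | none | looser |
| Day 1 serum | day -14 to 0 | day -14 to 0 | same |
| Month 7 serum | 21–49 days after dose 3 | 21–105 days after dose 3 | looser |
| Interfering deviations | excluded | kept | looser |
| Day 1 serostatus, seven other types | negative to that type | negative to that type | same |
| Day 1 serostatus, HPV 6 and 11 | negative to that type | negative to both | **stricter** |

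**Step 2: who is affected.** Take a patient who meets all the other PPI criteria.

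| Day 1 status | PPI-6 | ANSS-6 | PPI-11 | ANSS-11 |
|---|---|---|---|---|
| 6−, 11− | in | in | in | in |
| 6−, 11+ | in | **out** | out | out |
| 6+, 11− | out | out | in | **out** |
| 6+, 11+ | out | out | out | out |

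Only patients positive to exactly one of the two types are treated differently. One such patient in the data is enough to break containment.

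**Step 3: reproduce the plan's own figures.** Section 3.5.6 says of the HIV group "we expect to be able to use the data of at least 80 patients" for each type. It gives margins of 4.8% to 2.2% for seroconversion of 95% to 99%, and 6.6% for 90%. With margin = 1.96 × √(p(1−p)/n) and n = 80:

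- p = 0.95: 4.78%
- p = 0.99: 2.18%
- p = 0.90: 6.57%

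All three agree with the plan.

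**Step 4: possible size in the HIV group.** The Rationale for Amendment 1 gives baseline seropositivity of 13% to 45% across types. It gives no separate or joint figure for 6 and 11. Assume the same seropositivity s for both, 100 patients, and no other losses. The 20% case is the level that leaves the plan's 80 usable patients.

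- Single-type rule: 100(1−s)
- Both-negative rule: 100(1−s)² if independent, 100(1−s) if the same people are positive to both, 100(1−2s) if nobody is positive to both

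| s | Single-type | Both-negative: independent | Coincident | No overlap | Extra removed: independent (range) |
|---|---|---|---|---|---|
| 13% | 87 | 75.7 | 87 | 74 | 11.3 (0–13) |
| 20% | 80 | 64 | 80 | 60 | 16 (0–20) |
| 45% | 55 | 30.3 | 55 | 10 | 24.8 (0–45) |

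**Step 5: which set is larger.** Let r be the share of type-negative patients with three doses and serum at 21–105 days who also meet PPI's extra rules. Starting from 100 such patients before the serostatus rules and assuming independence, PPI = 100(1−s)r and ANSS = 100(1−s)². ANSS is the smaller set only if r > 1−s, that is, if PPI's extra rules remove less than 13%, 20% or 45% in the three cases. The plan does not give these losses.

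**Step 6: precision and possible shift.** At p = 0.95 the margin is 4.78% with 80 subjects and 1.96 × √(0.95 × 0.05/64) = 5.34% with 64.

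For the point estimate, take 80 single-type-negative patients with 76 seroconverted (95%) and remove 16:

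- if all 16 seroconverted: (76 − 16)/64 = 60/64 = 93.75%, a shift of −1.25 points
- if 90% of the 16 did (assumption): (76 − 14.4)/64 = 61.6/64 = 96.25%, a shift of +1.25 points

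**The case against.** The plan promises only a supportive analysis on ANSS. It specifies no formal PPI–ANSS comparison and nowhere requires one set to contain the other. For the other seven types a difference would also bundle several relaxations (dose, vaccination windows, serum window, deviations), so aligning the baseline rule does not isolate a single cause. The patient counts rest on assumed seropositivity and could be zero. In the 20% scenario the estimate moves by about 1.25 points, well inside the plan's 4.8% margin. Pairing 6 and 11 may be deliberate. The primary PPI analysis already does what the amendment rationale describes.

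Most of this stands as a limit on importance. The counts are illustrative, the likely shift is small, and the primary analysis is untouched. It does not remove the inconsistency. The relaxations for the other seven types all act in one direction and only add patients; for HPV 6 and 11 one rule works the other way. If there is a reason for pairing the types, the documents do not state it, and nothing in them explains why it would apply to the supportive set and not to the primary one.

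**Conclusion.** The concern holds, as a minor point. That ANSS fails to contain PPI for HPV 6 and 11 follows from the definitions and needs no assumption; in the data it shows whenever a patient who meets the PPI rules is positive to exactly one of the two types.

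The size does depend on assumptions. With equal seropositivity of 13%, 20% or 45%, the both-negative rule removes 11, 16 or 25 more per 100 HIV patients under independence. It removes none if the statuses coincide, and at most 13, 20 or 45. No seroprevalence is given for SOT patients, so the expectation that the HIV group is more affected rests on the eligibility criteria alone.

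What is lost is interpretability, since precision barely changes. ANSS still tests timing and deviations among patients negative to both types. The primary PPI estimates and the sample-size figures are unaffected.

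**What to change.** Use one baseline rule in both sets. In the ANSS definition, delete the sentence on HPV 6 and 11 and extend the sentence that follows from the remaining types to all nine. The type-specific rule of the PPI section, which the ANSS bullets already state, then governs every type, and ANSS contains PPI throughout.

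If the sponsor has a reason for pairing the two types, state it and report HPV 6 and 11 under the both-negative rule in PPI and ANSS alike, as a labelled sensitivity analysis. Make the change before database lock, so that the choice of rule cannot look post hoc.

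The cost is one sentence in the plan and at most one extra table for two types. No new data are needed. Under Baseline HPV Status (section 3.5.5.3) the plan says "A serum sample will be collected from all subjects at the Day 1 visit", for serostatus to all nine types.
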